8.7.2. Banked Biospecimens for Genetics

A 2-mL whole blood sample optimized for DNA isolation Prep D1.5 will be collected as local regulations and IRBs/ECs allow, if limits on blood volume collection have not been exceeded.

Banked biospecimens may be used for research related to drug response and DMD. Genes and other analytes (eg, proteins, RNA, non-drug metabolites) may be studied using the banked samples.

Unless prohibited by local regulations or IRB/EC decision, participants will be asked to indicate on the consent document whether they will allow their banked biospecimens to also be used to design and conduct research in order to gain a further understanding of other diseases and to advance science, including development of other medicines for patients. This component of the sampling banking is optional for participants; they may still participate in the study even if they do not agree to the additional research on their banked biospecimens. The optional additional research does not require the collection of any further samples.

See [Appendix 5](#) for information regarding genetic research. Details on processes for collection and shipment of these samples can be found in Laboratory Manual.

8.8. Biomarkers

Collection of samples for biomarkers research is also part of this study.

8.8.1. Specified Gene Expression (RNA) Research

Specified gene expression (RNA) research is not included in this study.

8.8.2. Specified Protein Research

Specified protein research is not included in this study.

8.8.3. Specified Metabolomic Research

Specified metabolomic research is not included in this study.

8.8.4. Banked Biospecimens for Biomarkers

A 1-mL whole blood (Prep B2.5), 1-mL whole blood (Prep B1.5), and 5-mL urine (Prep M4) samples will be collected as local regulations and IRB/ECs allow, if limits on blood volume collection have not been exceeded.

Banked biospecimens may be used for research related to drug response and DMD. Genes and other analytes (eg, proteins, RNA, nondrug metabolites) may be studied using the banked samples.

Unless prohibited by local regulations or IRB/EC decision, participants will be asked to indicate on the consent document whether they will allow their banked samples to also be used to design and conduct research in order to gain a further understanding of other diseases and to advance science, including development of other medicines for patients. This component of the sampling banking is optional for participants; they may still participate in the study even if they do not agree to the additional research on their banked samples. The optional additional research does not require the collection of any further samples.

See [Appendix 5](#) for information regarding genetic research. Details on processes for collection and shipment of these samples can be found in Laboratory Manual.

8.8.5. Viral Vector Shedding Analysis

Whole blood (1.8 mL), saliva (4.2 mL), and urine (7.2 mL) samples for viral vector shedding kinetics will be collected in approximately the first 45 treated participants (approximately 30 treated with fordadistrogene movaparvovec and approximately 15 treated with placebo). Potential visits at which samples are to be collected are detailed in the **SoA**. For each of the approximately first 45 treated participants, sample collection for a particular matrix (sample type) will be stopped when at least 2 consecutive negative results are observed in that matrix. An unblinded qualified Sponsor representative, independent and firewalled from the study team, will review the viral vector shedding results for each participant on an ongoing basis and will communicate with the sites when sampling in a given matrix for each participant should be stopped. The viral vector shedding results will not be shared with the sites. To maintain the study blind, the unblinded qualified Sponsor representative will select Cohort 2 participants (as available) to also have the sampling of the same matrix stopped every time the sampling in a given matrix is stopped for a Cohort 1 participant. An attempt will be made to match these Cohort 2 participants to the specific matrix and timing of Cohort 1 participants.

Detailed collection, processing, storage, and shipment instructions will be provided in the central laboratory manual to maintain sample integrity for each sample type.

The assay reflects the presence of DNA unique to fordadistrogene movaparvovec. Results below the lower limit of quantification (LLOQ) will be reported as below the limit of quantification (BLQ) and will be considered negative. Additionally, saliva and urine samples for all time points from a subset of participants will be analyzed for deoxyribonuclease-resistant particles.

As part of understanding the disease and advance science, samples may be used for further characterization and/or evaluation. These data will be used for internal exploratory purposes and will not be included in the clinical study report. Samples collected for this purpose will be retained in accordance to local regulations and if not used, will be destroyed.

8.8.6. Study C3391007 Household Contact Immunogenicity

To further understand the development of antibodies to AAV9 (ie, seroconversion) due to household contact with a participant treated with fordadistrogene movaparvovec, a study may be performed under a separate protocol. Seroconversion rates from this separate study may be estimated prior to unblinding (either for an interim analysis or the primary analysis) of study C3391003. The integrity of the C3391003 study blind will be maintained by the use of an independent, external team of statistician(s) and programmer(s) to estimate the seroconversion rates. Only summary seroconversion rates will be communicated.

8.9. Health Economics

8.9.1. Healthcare Resource Utilization Questionnaire – Caregiver (HRU:CG)

The Healthcare Resource Use questionnaire is a 4-item, caregiver-completed measure that asks about healthcare resource utilization related to their child's use of healthcare

professionals, emergency room visits, and hospitalizations related to DMD. Caregivers are also asked to estimate out-of-pocket costs related to healthcare resource utilization. The recall period is the past 3 months.

8.9.2. Work Productivity and Activity Impairment DMD Questionnaire – Caregiver (WPAI:DMD Caregiver)

The WPAI:DMD Caregiver is a 6-item, caregiver-completed questionnaire that measures the effect of a child being diagnosed with DMD on caregiver work productivity and impairment. The WPAI:DMD Caregiver yields four scores: absenteeism (work time missed); presenteeism (impairment at work/reduced on the job effectiveness); work productivity loss (overall work impairment/absenteeism plus presenteeism); and activity impairment. Each score is expressed as a percentage (0-100%) with higher numbers indicating greater impairment and less productivity (Reilly et al, 1993).⁶⁵ The recall period is the past 7 days.

8.10. Immunogenicity

8.10.1. Neutralizing Antibody to AAV9

Blood samples for analysis of NAb to AAV9 will be collected. Detailed collection, processing, storage, and shipment instructions will be provided in the central laboratory manual.

Samples will be analyzed using validated analytical methods in compliance with Pfizer standard operating procedures (SOP).

As part of understanding of the immunogenicity of the fordadistrogene movaparvovec, samples may be used for further characterization and/or evaluation of the bioanalytical method. These data will be used for internal exploratory purposes and will not be included in the clinical report. Samples collected for this purpose will be retained in accordance to local regulations and if not used, will be destroyed.

8.10.2. ELISpot

Blood samples to provide peripheral blood mononuclear cells for analysis of cellular immune responses to mini-dystrophin and AAV9 will be collected.

Detailed collection, processing, storage, and shipment instructions are provided in the central laboratory manual.

As part of understanding of the immunogenicity of fordadistrogene movaparvovec, samples may be used for further characterization and/or evaluation of the bioanalytical method. In addition, residual of these samples may be used for the evaluation of exploratory biomarkers of immune response. These data will be used for internal exploratory purposes and will not be included in the clinical report. Samples collected for this purpose will be retained in accordance to local regulations and if not used, will be destroyed.

8.10.3. Anti-drug Antibodies

Blood samples for analysis of anti-transgene (mini-dystrophin) and anti-AAV9 antibodies will be collected. However, these will only be tested if clinically indicated (eg, clinical immune response to fordadistrogene movaparvovec).

Detailed collection, processing, storage, and shipment instructions will be provided in the central laboratory manual.

Samples will be analyzed using validated analytical methods in compliance with Pfizer standard operating procedures.

As part of understanding of the immunogenicity of the fordadistrogene movaparvovec, samples may be used for further characterization and/or evaluation of the bioanalytical method. These data will be used for internal exploratory purposes and will not be included in the clinical report. Samples collected for this purpose will be retained in accordance to local regulations and if not used, will be destroyed.

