2.3.2. Immunogenicity Risk Assessment

Humoral and cellular immune responses against both the vector and the transgene may negatively impact the safety and efficacy of gene therapy and will be carefully monitored [[Mingozzi et al., 2011](#)].⁴⁸ NAb to the vector could significantly reduce muscle cell transduction, and therefore participants with pre-existing NAb are excluded from the study. An immune response to the vector and/or the transgene following treatment can lead to inflammation of tissues that are transduced, such as liver, muscle, and heart, and/or to a systemic immune reaction, such as complement activation, that may result in damage to blood, renal, and possibly other systems.

In order to reduce the possibility of an immune reaction, participants will receive a single IV administration of methylprednisolone prior to the infusion of IP, followed by a protocol-mandated regimen of daily oral glucocorticoids for 3 months, as described in [Section 6.5.1](#).

In a number of on-going or completed clinical studies with AAV-based vectors, the most consistent treatment-emergent adverse reaction reported has been elevations in liver enzymes. Most reported events have resolved with the administration of glucocorticoids (Nathwani).⁴⁹ To reduce the risk of liver injury associated with fordadistrogene movaparvovec, participants will receive a single IV administration of methylprednisolone prior to the infusion of IP, followed by a protocol-mandated regimen of oral glucocorticoids for 3 months. Liver injury will be monitored closely using laboratory assessments, including serum glutamate dehydrogenase (GLDH), which is a liver-specific enzyme and is not increased in the setting of muscle disease as is the case for AST and ALT (See [Appendix 6](#)).

Cases of skeletal muscle and cardiac injury have been observed in clinical studies of fordadistrogene movaparvovec. The potential for skeletal muscle injury is monitored primarily by physical signs and symptoms, and by measurements of CK, that are monitored on an ongoing basis by the unblinded medical monitor (see [Section 6.3.3](#)). The potential for cardiac injury is monitored using cardiac troponin I (see [Section 8.2.7](#)). Participants (and/or caregivers) should be instructed to contact the site if signs and symptoms of skeletal muscle and/or cardiac injury are observed (see [Section 8.2.11](#)).

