To characterize the skills either improved or maintained, based on the individual items of the NSAA, in participants treated with fordadistrogene movaparvovec as compared to placebo.	Number of skills either improved or maintained at Week 52 based on the individual items of the NSAA.	
To characterize the 10-meter run/walk velocity in participants treated with fordadistrogene movaparvovec as compared to placebo.	Change from Baseline at Week 52 in the 10 meter run/walk velocity.	
To characterize the rise from floor velocity in participants treated with fordadistrogene movaparvovec as compared to placebo.	Change from Baseline at Week 52 in the rise from floor velocity.	
To characterize the functional health status in participants treated with fordadistrogene movaparvovec as compared to placebo.	Change from Baseline at Week 52 in the Modified Pediatric Outcomes Data Collection Instrument (PODCI): Transfer and Basic Mobility Core Scale (Pediatric Parent).	
	Change from Baseline at Week 52 in the Modified PODCI: Sports and Physical Functioning Core Scale (Pediatric Parent).	
Tertiary/Exploratory:	Tertiary/Exploratory:	
To assess the systemic immune response (humoral and cellular) to mini-dystrophin in participants treated with fordadistrogene movaparvovec.	Immune response (eg, anti-drug antibodies (ADA) and enzyme-linked immune absorbent spot (ELISpot) to mini-dystrophin through Year 1 Week 52.	N/A
To assess the systemic immune response (humoral and cellular) to the AAV9 capsid in participants treated with fordadistrogene movaparvovec.	Immune response (eg, ADA, ELISpot, and, NAb) to AAV9 through Year 1 Week 52.	N/A
To characterize the change in ankle range of motion in participants treated with fordadistrogene movaparvovec as compared to placebo.	Change from Baseline at Week 52 in passive ankle range of motion (dorsiflexion).	N/A
To characterize real-life function in participants treated with fordadistrogene movaparvovec as compared to placebo.	Change from Baseline at Week 52 in real-life function parameters as assessed by actigraphy.	N/A

Objectives	Endpoints	Estimands
To tabulate loss of ambulation in participants treated with fordadistrogene movaparvovec as compared to placebo.	Loss of ambulation through Week 52.	N/A
To characterize pulmonary function in participants treated with fordadistrogene movaparvovec as compared to placebo.	Change from Baseline at Week 52 in %pFVC.	N/A

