6.3.3. Sensitive Clinical Data

Select safety and immunogenicity results

In order to prevent the functional unblinding of the treatment assignment, the results of the following assessments will not be shared with the study team or the site after Year 1 IP administration and throughout the blinded portion of the study:

- CK;
- AST and ALT;
- NAb to AAV9 (See [Section 7.1](#));
- ELISpot to AAV9 and mini-dystrophin;
- ADA to AAV9 and mini-dystrophin;
- C3 and C4.

An unblinded medically qualified monitor (medical monitor) will review the results of CK, AST and ALT, NAb to AAV9, and ADA to mini-dystrophin for each participant on an ongoing basis and will decide if any result(s) should be repeated and/or shared with the site and the study team, due to a judgement that the results could reflect a safety issue (eg, liver injury, myositis, other immunological reaction).

If a participant in Cohort 2 presents with a positive test for NAb to AAV9 on the sample taken at the Day 34 (Visit 13) he will be withdrawn from the study given that it would already be determined at that time that he is not be eligible for fordadistrogene movaparvovec administration at Year 2. If this situation occurs while the study is still accruing participants, an additional 2 participants may be randomized for each Cohort 2 participant who is withdrawn.

Additionally, if the threshold of laboratory abnormalities for a potential drug-induced liver injury (DILI) case has been met (see [Appendix 6](#)), the results for ALT and AST will be shared with the site and the study team until the potential DILI has been investigated and it is considered resolved.

If a clinical event occurs that, in the opinion of the Sponsor and/or the Investigator, could be due to an immunological reaction, additional ad-hoc assessments of NAb to AAV9, ADA to AAV9 and mini-dystrophin, ELISpot to AAV9 and mini-dystrophin may be conducted if

considered indicated by the Sponsor and/or the Investigator for the interpretation and/or the management of the immunological reaction. The results of these tests will be shared with the site and the study team.

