10.2. Appendix 2: Clinical Laboratory Tests

The following safety laboratory tests will be performed at times defined in the **SoA** section of this protocol. Additional laboratory results may be reported on these samples as a result of the method of analysis or the type of analyzer used by the clinical laboratory; or as derived from calculated values. These additional tests would not require additional collection of blood. Unscheduled clinical laboratory measurements may be obtained at any time during the study to assess any perceived safety concerns.

Table 3. Protocol Required Safety Laboratory Assessments

CENTRAL LABORATORY TESTING		
Clinical Safety		
Hematology	Urinalysis	Other
Hemoglobin Hematocrit Red blood cell (RBC) count and morphology Platelet count White blood cell count (and morphology as applicable) Total neutrophils (Abs) Absolute neutrophils Eosinophils (Abs) Monocytes (Abs) Basophils (Abs) Lymphocytes (Abs) Red blood cell indices (mean corpuscular volume, mean corpuscular hemoglobin, mean corpuscular hemoglobin concentration)	pH Glucose (qual) Protein (qual) Blood (qual) Ketones Nitrites Leukocyte esterase Microscopy and culture ^a	Prothrombin time (PT) activated partial thromboplastin time C-reactive protein Lipase Amylase Cystatin C Haptoglobin ^b
Chemistry and Hepatic Safety		
BUN and Creatinine Glucose Calcium Sodium Potassium Chloride Total CO ₂ (Bicarbonate) AST, ALT Total Bilirubin (direct and indirect bilirubin) Alkaline phosphatase Uric Acid Albumin Total protein Serum Phosphorus Gamma glutamyl transferase (GGT) Glutamate dehydrogenase (GLDH)		

Table 3. Protocol Required Safety Laboratory Assessments

For Screening (Visit 1) and Day 360 (Visit 19) Only	
International normalized ratio (INR) Hepatitis A virus (anti-HAV) immunoglobulin M Hepatitis B surface antigen Hepatitis C antibody	
For Post IP Intensified Safety Monitoring (at Year 1 and Year 2)	
Complement biomarkers eg, C3 and C4, additional exploratory ^c Haptoglobin- analyzed by local laboratory on Days 2 and 4 (Visits 4 and 5) in Year 1 and on Days 391 and 393 (Visits 21 and 22) in Year 2 for sites in Japan. Urine biomarkers	
Other Assessments	
Immunogenicity: NAb to AAV9; ELISpot to AAV9; ADA to AAV9; ELISpot to mini-dystrophin; ADA to mini-dystrophin	
Viral vector shedding (whole blood, saliva, and urine)	
Cardiac troponin I	
Creatine kinase	
Conditional Testing	
Genetic screening for aHUS-Central Laboratory , if needed as per Section 6.5.1	

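### Section 8.10.3 tests anti-drug antibodies only on clinical indication, while Section 6.3.3 has the unblinded medical monitor review ADA to mini-dystrophin for every participant on an ongoing basis

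*Protocol*

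**What the plan says.** Section 8.10.3 of the protocol sets the rule for anti-drug antibodies. It names both analytes: "Blood samples for analysis of anti-transgene (mini-dystrophin) and anti-AAV9 antibodies will be collected". The next sentence limits what happens to those samples: "However, these will only be tested if clinically indicated (eg, clinical immune response to fordadistrogene movaparvovec").

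Section 6.3.3 withholds certain results from the site and the study team during the blinded period and gives an unblinded medical monitor the task of looking at some of them. That person "will review the results of CK, AST and ALT, NAb to AAV9, and ADA to mini-dystrophin for each participant on an ongoing basis" and decides whether a result should be repeated or released because it may signal a safety problem. The examples given are liver injury, myositis and other immunological reactions. The same section provides separately for suspected immunological events, after which "additional ad-hoc assessments of NAb to AAV9, ADA to AAV9 and mini-dystrophin, ELISpot to AAV9 and mini-dystrophin may be conducted".

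Three other places bear on the point:

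- Section 2.3.2 says of humoral and cellular responses that "immune responses against both the vector and the transgene may negatively impact the safety and efficacy of gene therapy and will be carefully monitored".
- Appendix 2 opens Table 3 with "The following safety laboratory tests will be performed at times defined in the" Schedule of Activities, and lists under other assessments "Immunogenicity: NAb to AAV9; ELISpot to AAV9; ADA to AAV9; ELISpot to mini-dystrophin; ADA to mini-dystrophin".
- Section 3.1 has exploratory endpoints that name ADA as an example, to mini-dystrophin and also to the vector: "Immune response (eg, ADA, ELISpot, and, NAb) to AAV9 through Year 1 Week 52".

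**The concern.** Section 8.10.3 makes a clinical trigger the condition for any ADA assay. Section 6.3.3 assumes that ADA-to-mini-dystrophin results exist for every boy and arrive continuously. A laboratory working from 8.10.3 would hold the samples, and the monitor working from 6.3.3 would wait for results that never come.

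Section 2.3.2 explains why this matters. An immune response to the vector or the transgene can inflame transduced tissue, including liver, muscle and heart, and skeletal muscle and cardiac injury have already been seen in clinical studies of this product. Under 8.10.3, an antibody response to the transgene would be looked for only after somebody already suspected a problem, for example after a rise in CK or transaminases. Any exploratory summary of ADA would then describe boys selected because they had an indication, not the treated group.

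**Working it through.** No power or error-rate arithmetic applies. The check sets the rules side by side and counts what they affect.

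**1. Do the two rules cover the same analyte?** Yes. Section 8.10.3 names the anti-transgene and anti-AAV9 antibodies and applies the restriction to both, so ADA to mini-dystrophin is not exempt. Section 6.3.3 names ADA to mini-dystrophin explicitly.

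**2. Can both be followed?**

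| | Section 8.10.3 | Section 6.3.3 |
|---|---|---|
| Who has a result | Boys with a clinical indication | Each participant |
| When | After the indication | Ongoing |
| Event-triggered testing | The only testing | Additional to other testing |

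They disagree on every row. Section 6.3.3 also lets the monitor ask for a result to be repeated, which presupposes a first result.

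**3. Which rule fits the rest of the protocol?** The Year 1 Schedule of Activities (Section 1.3.1) has ADA draws at fixed visits, and footnote ff marks three of them as being for mini-dystrophin alone. Scheduled draws do not settle the matter by themselves. Footnote cc shows that the protocol can collect a sample routinely (baseline NAb) and analyze it only under a stated condition. But there the condition is written into the schedule, whereas footnote ff only limits the analyte. In Appendix 2, ADA is not under the conditional-testing heading, which holds the aHUS genetic screen and NT-ProBNP/BNP. This evidence is modest, and it leans towards 6.3.3.

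**4. What would be lost?**

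- Monitor's review list in 6.3.3: CK, AST, ALT, NAb to AAV9, ADA to mini-dystrophin = 5 analytes. Directed at the transgene: 1 (ADA to mini-dystrophin). NAb is directed at the capsid; the other three are enzymes.
- Immunogenicity assays in Appendix 2: NAb to AAV9, ELISpot to AAV9, ADA to AAV9, ELISpot to mini-dystrophin, ADA to mini-dystrophin = 5. Antibody assays against the transgene: 1.
- ELISpot to mini-dystrophin also measures a transgene response. It is among the results withheld under 6.3.3 but is not in the monitor's review list, and Year 1 has 1 scheduled post-dose sample for it (Day 60).

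**5. How many samples?** The Year 1 ADA row, after Screening and before the Early Discontinuation column, has 3 draws for mini-dystrophin only plus 3 for both antigens:

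- per boy: 3 + 3 = 6
- Cohort 1, about 66 boys: 6 × 66 = 396
- both cohorts, about 99 boys: 6 × 99 = 594

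The cohort sizes are the Full Analysis Set targets and exclude siblings. The first total covers boys who receive active vector in Year 1. The second covers everyone to whom the contradictory wording applies.

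**The case against.** The best case for the protocol runs as follows.

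- **Section 6.3.3 is about blinding.** It governs who may see results, not which samples are assayed, so it could mean that the monitor reviews ADA results as and when they are generated. This reading is strained: it leaves the references to each participant and to ongoing review with little meaning.
- **The word additional need not imply routine testing.** The ad hoc sentence also covers ADA to AAV9 and ELISpot, which are outside the monitor's list, so it may mean only unscheduled. That is fair, and the sentence is supporting evidence, not proof.
- **Appendix 2 and Section 2.3.2 are weak support.** NAb and vector shedding sit under the same Appendix 2 heading yet are subject to conditions or limits elsewhere, and Section 2.3.2 names no assay or frequency. This stands. The contradiction rests on 8.10.3 against 6.3.3.
- **The harm is narrow and conditional.** It arises only if 8.10.3 is the rule followed. Section 2.3.2 names signs, symptoms and CK as the primary monitoring for skeletal muscle injury and troponin I for cardiac injury. The samples are still drawn and can be assayed later. This stands too, and it limits the severity.
- **The conflict could be removed the other way,** by deleting ADA from 6.3.3. That would make the text consistent, but it would give up a safety review the protocol promises in a disease and product where immune-mediated muscle injury is a stated risk.

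The central laboratory manual might contain a clear instruction. However, 8.10.3 refers to it only for collection, processing, storage and shipment, and a manual would not correct a contradiction in the protocol.

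**Conclusion.** The contradiction is real for ADA to mini-dystrophin and is unresolved in the protocol. If 8.10.3 is followed, the monitor has no routine results for 1 of the 5 analytes in the 6.3.3 review list, the only one directed at the transgene, and any exploratory ADA summary rests on boys selected by indication. The samples with contradictory status number 6 per boy in Year 1, about 396 in Cohort 1. This count does not measure harm, and the effect on safety or on an ADA summary cannot be estimated from the document.

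The conclusion assumes that the indication rule in 8.10.3 means what it says and that the 6.3.3 review is of actual results for all participants. It does not extend with the same force to ADA to AAV9, which is outside the monitor's review list and otherwise appears only in the general Appendix 2 lead-in and in exploratory endpoints given as examples. The primary and secondary endpoints are untouched. The text should be corrected, but the point does not threaten the trial's main result.

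**What to change.** Amend Section 8.10.3 to say that scheduled ADA-to-mini-dystrophin samples are assayed irrespective of clinical indication, that the results go to the unblinded medical monitor under Section 6.3.3, and that event-triggered tests are additional. The indication rule can stay for ADA to AAV9 if that is the intention, but its results should then not be presented as an incidence among all treated participants.

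The cost is one sentence in an amendment and the assay cost on samples already scheduled to be drawn. It needs no new visits and no added blood volume, and the blind is unaffected because the results stay with the unblinded monitor.
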